Project title: PRImary care Streptococcal Management study (PRISM) (05/10/01) Rapid tests for streptococcal sore throat) protocol (version 4 10/09/08)

Planned investigation

Our Research Objectives are:

1) to assess which RADT is the most accurate in predicting the presence of group A streptococcus by throat swab in a clinical sample from primary care;

2) to estimate the error from sampling bias by performing parallel standardised in vitro studies;

3) to assess the validity of a scoring system based on the throat swab as the reference standard (such as the Centor criteria) in a UK population;

4) to assess the effectiveness and cost-effectiveness of rapid tests when compared to clinical scoring rules and delayed antibiotic prescription;

5) to explore the effect of additional benefit from the RADT use on GP diagnostic prediction accuracy and treatment decisions.

Existing research.

Overview. Antibiotic resistance is a major threat to public health: the key to reducing the risk from antibiotic resistance is to reduce use for those patients who will not benefit. Equally it is important for patients and society – particularly in terms of sickness absence - not to deny health benefit to those who will suffer severe or prolonged symptoms, and where possible to find effective alternatives to antibiotics. Sore throat is the commonest URTI managed in primary care, and primary care is where the majority of antibiotics are prescribed i.e. where the battle to improving targeting of antibiotics must be won.

This project, in providing key information about the most effective way of targeting antibiotics, has the potential to make a significant impact in improving clinical diagnosis for everyday clinical practice for patients with URTI. URTI is the only respiratory infection where there are good range of diagnostic alternatives (including both clinical scores and near patient tests), although there have been very few randomised trials of diagnostic methods. The impact is likely to be in improving the short term health - by minimising unnecessarily severe or prolonged symptoms and reducing side effects from unnecessary antibiotics; minimising the long term public health risks of inappropriate antibiotics; and providing a model for different management strategies for other RTIs.

Antibiotics: a Cochrane review suggests modest symptomatic benefit of antibiotics for sore throat and that antibiotics prevent complications¹, which is supported by recent ecological data.² The solution is not to increase antibiotic use indiscriminately but to better identify individuals who are likely to benefit.

Better targeting? Sore throat is one of the rare respiratory infections where there are several reasonable diagnostic alternatives. Showing which of these help best in managing symptoms and minimising inappropriate antibiotic prescribing will be invaluable for the management of sore throat – where antibiotics are still prescribed in 50-60% of patients³. Demonstrating what works in URTI may also be a model for what is possible for other RTIs. The available methods of diagnosis have been systematically reviewed ⁴:

Throat swab: this is the standard diagnostic method and the traditional clinical 'gold standard', but results take days, it increases costs, may miss significant infection (due to the organisms in the tonsillar crypts being different to those on the surface) and is not specific (due to prior 'carriage' of organisms in the pharynx⁴).

Near patient tests (NPTs). Rapid streptococcal antigen detection tests (RADTs) are a practical alternative to throat swabs in managing sore throat. Although RADTs (and swabs) have the same limitations as throat swabs – i.e. they cannot differentiate infection from prior carriage, and may miss infection in the tonsillar crypts - they nevertheless have the potential to halve antibiotic prescribing for acute sore throat, and significantly improve targeting of antibiotics.^{4 5 6:7} The potential disadvantage of rapid tests is that they may foster the belief that patients need to see their doctor in order to have the test in order for decisions to made about treatment i.e. potentially 'medicalising' URTI⁸.

Which RADT and how to assess them? The MHRA⁹ recently identified five RADTs marketed in the UK. Evidence from the previous literature suggests:

- **accuracy of RADTs** has mostly been evaluated in microbiological labs⁹(67% of studies); the fewer clinical studies have rarely compared all the commonly available tests in the UK, nor among typical UK primary care populations which is particularly important in view of 'spectrum bias' when not using primary care populations^{10;11}; thus a clinical sample in the intended setting is important to assess overall performance characteristics of RADTs;
- **sampling bias** has rarely been fully addressed: the key issue determining performance of RADTs is the number of organisms harvested since the performance is strongly related to the number of colonies growing on the agar plate¹²; furthermore, the agreement of a test versus standard is not likely to exceed the comparison of the standard versus itself¹³ and in the case of throat swabs well taken throat swabs taken from the same individual only achieve 83%-91% sensitivity when compared to each other¹⁴⁻¹⁶;

finally, since the sensitivities from previous studies comparing RADTs to throat swabs suggest that the better RADTs are likely to be in the above range (i.e. 85%+), sampling bias is likely to provide the main error in any clinical validation study of RADTs, and a clinical validation study alone may well not provide definitive answers regarding the best RADT to use; to get round this problem the performance in standardised conditions i.e. in vitro performance can also be estimated¹⁷;

• **comparison of ease of use** by practitioners have rarely been performed.¹⁷

Any assessment of an RADTs therefore has to assess performance in clinical settings (which includes the performance of the test in the intended setting and sampling error), performance excluding sampling error (by assessing performance in standardised conditions), and ease of use (time taken, ease of use, clarity of reading), **Clinical scoring methods.** Existing clinical scores also have most promise to be useful in practice ^{4 5 6} - the major candidate being the 'Centor' criteria, which has been operationalised in two recent primary care trials^{18 22} as 3 out of 4 of pus, cervical nodes, a history of fever and no history of cough.

Is it plausible that benefit exists from using clinical scores?: Even with the key limitations of validity identified above, preliminary indirect evidence indicates that existing scores may predict benefit. Clinical scoring methods which predict bacterial infection not only have the potential to predict symptomatic benefit from antibiotics, but also are likely to predict an increased risk for complications¹⁸²². The trials included in the systematic review suggest 8-12 hours symptomatic benefit from antibiotics, whereas in two trials among selected patients with 3 out of the 4 'Centor' criteria, 1-2 days mean benefit was documented.¹⁸ However this is indirect historical comparison: the patients in the systematic review were not necessarily comparable, and historical comparisons are notoriously unreliable. Other problems with the Centor criteria are:

- that there has been no robust validation in a typical UK population (i.e. the issue of spectrum bias since studies did not use typical primary care populations; the study in Ireland (Dobbs^{6;7}) with a similar population used univariate analysis only and thus was over-inclusive);
- the criteria very probably have low specificity in primary care populations 44% in a recent Canadian study⁷ which would result in rather high rates of overall antibiotic use (46% of adults).⁷

This would suggest that using the Centor criteria alone will not significantly improve antibiotic targeting; that a modified approach should be considered based on validation using UK data if the Centor criteria are to be used. Once the best RADT and best clinical scores have been decided, this does not necessarily translate into predicting benefit for patients. It is thus crucial to test the performance of the best performing RADT and clinical score in a pragmatic trial against each other and against other treatment strategies, especially since the RADT strategy is likely to increase costs and may have 'medicalising' consequences.

MRC DESCARTE study. Since the submission of this application our group has also been funded by the MRC to undertake the DESCARTE study (DEcision rule for the Symptoms and Complications of Acute Red Throat in Everyday practice). This is a large cohort study and is very simple – using a one page tick box clinical proforma only, and then subsequent documentation of adverse events. The great advantage to PRISM of the overlap between the studies is that we will be in a unique position of being able to compare the characteristics of patients and outcomes in PRISM with a wider clinical population to assess issues of generaliseability and spectrum bias. Furthermore both studies will provide important and overlapping scientific information; the results of DESCARTE (which will tell us about 'at risk' groups of patients) will be used in assessing the management and symptomatic outcomes of such 'at risk' patients in phase II of PRISM; conversely PRISM will allow assessment of the potential for rapid tests and clinical scores to target antibiotics to individuals at risk of adverse events in the DESCARTE data set. Providing data to address this issue (i.e. the potential for the PRISM strategies to modify adverse events) will provide an additional dimension to PRISM that would not be possible unless DESCARTE was funded, and is made possible by compatible clinical proformas. We will be able to include the potential for the PRISM strategies to modify adverse events in our modelling exercise at the end of phase II. Thus there are significant scientific advantages in the overlap between studies and little direct competition between these studies.

Research methods

Design Summary.

This study is in two phases:

Phase I is a validation and development phase and will include five components:

1) a clinical study to determine the ease of use and overall the performance in clinical settings of the 5 currently available RADTs using the throat swab as the reference standard;

2) nested data from the same sample will be used to assess whether the a scoring system based on the throat swab as a reference standard (such as the Centor criteria) requires modification

3) in vitro studies to assess the performance of RADTs in standardised conditions and thus assess the issue of sampling bias when using RADTs;

4) a qualitative study to explore patients and GPs' perceptions about the use of RADTs;

Phase II. This trial will compare management using a) the best RADT defined from phase 1 compared with b) a clinical scoring rule (a Centor-like criteria based on predicting the results of throat swabs) and c) with the empirical strategy of delayed antibiotic prescription. Phase II will include a cost consequences analysis, which along with a review of the longer term effects of reduced antibiotic resistance will feed into a simple cost effectiveness model.

Methods: Phase 1

1) Clinical study of RADTs.

Inclusion: Adults/children aged 5 and over presenting with acute sore throat (2 weeks or less; and with some abnormality of examination of the throat – i.e. erythema and or pus - as in our previous studies in primary care¹⁹). Although there some evidence that those presenting acutely are more likely to have bacterial infection²⁰ and more likely to benefit from antibiotics it is important that the performance and use of tests reflect the generaliseable population presenting in primary care. Exclusion: other non infective causes of sore throat (e.g. apthous ulceration, candida, drugs), unable to consent (e.g. dementia, uncontrolled psychosis)

Throat swabs. Despite the theoretical potential for either overgrowth, failed growth, or poor operator performance of tests, evidence suggests that

- the performance of a test based on a swab done in the doctors practice are equivalent to the results from the same swab in the laboratory^{9;21;22};
- one swab can also be used for more than one plate providing identical numbers of colonies on up to 5 plates ^{9;23};
- two double swabs can be done in adults.¹⁴

Thus any clinical validation study can take advantage of using two double swabs in each adult, using the same swab for both RADT and culture, and can minimise practice disruption by letting laboratory staff perform the tests. In adults two double throat swabs will be taken (allowing four tests for each adult), but in children only one double swab is likely to be acceptable.

Based on the above evidence each swab will be sent to a central laboratory (which was shown to be feasible in piloting). Each swab will be used for both conventional microbiology (culture and sensitivity – using Todd-Hewitt broth, which provides the best reference standard in this context⁹), and also for one rapid test. Our piloting in 60 patients has also confirmed the that using the same swab for one RADT and the culture is both feasible, and minimises sampling variation.

Analysis. The rationale of the rapid test is to replace the need for a throat swab, and obtain the same clinical information as the throat swab, but in a much more timely manner. Thus the primary analysis of the accuracy of the RADTs will be the analysis of 2x2 tables comparing RADTs with the results of the throat swab as the reference standard, calculating sensitivity, specificity, predictive values and likelihood ratios.

The criteria for choosing RADTs are a) acceptable sensitivity (>80%) from previous in vitro or clinical studies (based on the systematic review by the MHRA⁹ and the recent French Agency assessment¹⁷) b) ease of use¹⁷ c) availability and EU 'CE' marking. In terms of availability in the UK and CE marking, a recent review this year by the MHRA identified 5 tests as being available and marketed in the UK⁹ (Signify Strep A (Abbott); Directigen 1,2,3, (Beckton /Dickinson);OSOM Ultra Strep A (Genzyme); Quickvue in line (Quidel) Strep A OIA MAX (Thermo Biostar)). However, since the MHRA review Directigen 123 and Signify Strep A are no longer available. Instead of Abbott Signify strep A we propose using the better performing Abbott Test pack plus Strep A ^{17 9} - which superseded the Signify test and is now marketed by Unipath as IMI Test Pack plus Strep A. The Directigen test we propose replacing with Streptatest (Dectrapharm, Strasbourg) which is available for UK use, CE marked, and performed very well in the French Health Products Safety Agency tests¹⁷. Streptatest

performed very well both the *in vitro* studies (in the top 3), and was also rated as easiest to use of all 16 tests compared. All our proposed tests performed acceptably for ease of use (range 24-35 out of a maximum 38, with the OIA max test performing worst and the Streptatest best) ¹⁷ and sensitivity. ^{17 9} As the Strep A OIA Max test is not designed as a 'point of care' test it will be replaced with the Clearview Exact Test (Unipath).

Summary of performance of proposed rapid tests for phase I clinical study								
of Ease of use score fu/ml) (maximum 38) ¹⁷								
35 no data ¹⁷ (similar tests averaged 30+)								
No data								
34								
28								
f								

*The studies were mostly not based in primary care and for the few clinical studies that have been performed in typical primary care settings the sensitivities are lower²⁴ than reported in the review⁹

Sample size. Most RADTs are very specific⁹. Sensitivity is the limiting factor, and the sensitivity from better performing previous studies is in the range of 80-90%.⁹ However we will be comparing a rapid test versus the results from the same throat swab which should provide higher sensitivities. Assuming 25% of the sample have streptococcus (based on our piloting) and a sensitivity of 85%-95% for the best RADT to estimate, with 95% confidence, sensitivity to within +/-5% (i.e. to be confident that the sensitivity is not less than 80% which would be less useful clinically) then 73 to 196 samples with streptococcus are required for each RADT (see table below), or 292-784 in total, 1460- 3920 allowing for the 5 RADTs, or 1500-4000 allowing for some leeway in the assumptions. If each adult provides four comparisons and each child two, then 400-1200 patients are required. Thus our minimum sample size is 438 and maximum 1176.

Sample size to estimate sensitivity with 95% confidence intervals of +/-5%

	Sensitivity		
	85%	90%	95%
Sample with streptococcus present	196	139	73
Sample for each RADT	784	556	292
(assuming 25% have streptococcus)			
Total number of tests (for 5 RADTs)	3920	2780	1460
Number of patients required (assuming two	1176	834	438
double swabs in adults and one double swab in			
children)			

²⁾ Clinical rule and clinical outcomes.

• Development of Clinical rule.

Confirming the validity of the Centor criteria in a modern UK primary care population. This study provides an opportunity to modify a clinical rule (such as Centor) which aims to predict the results of throat swabs. The rationale for this is that there have been no UK studies which have independently predicted the presence of Streptococcus (the Dobbs score used univariate analysis only, hence was over inclusive and rather unwieldy⁶); furthermore multivariate analysis of our pilot data in 120 individuals suggest the key independent variables to predict the presence of streptococcus were a history of fever at any time in the illness, a history of fever in the last 24 hours, the absence of cough, anterior cervical glands and muscle aches i.e. different from Centor. There are no additional costs to this aspect of the study since we will be documenting clinical details and taking throat swabs anyway

Clinical measures. Baseline proforma. In order to develop a clinical rule to predict bacterial infection, clinical features need to be compared with the results of the throat swab. GPs/Nurses will fill in the clinical details at baseline. This will consist of a single clinical sheet documenting baseline clinical data. We will collect data at presentation on temperature (using tempadot thermometers), the presence and severity of baseline symptoms (sore throat, difficulty swallowing, fever during the illness, runny nose, cough, feeling unwell, diarrhoea, vomiting, headache, muscles ache, abdominal pain, sleep disturbance, interference with normal activities) on 4

point Likert scales (none, a slight problem, a moderately bad problem, a bad problem), and the presence of signs (pus, nodes, tender nodes, temperature) based on previous clinical scores^{25 6 26 18}. The severity of symptoms not simply their presence is probably important: in piloting among 60 patients we have shown that the severity of symptoms rather than the presence of symptoms predicts bacterial infection which we documented by a four fold rise in antibody titres.

• Other clinical outcomes.

Symptom diary. Patients will fill a validated symptom dairy (as in phase 2). As in previous studies patients will be contacted when the research centre has received the consent form to check there are no problems filling in diaries.

If no diary is received after 2 - 3 weeks, one mailed reminder will be sent using a brief questionnaire containing the key diary items; if no diary or questionnaire has been returned a brief phone call will clarify the duration and severity of symptoms and whether antibiotic were used; this method has been shown to be both acceptable to patients and allows significantly less bias from low response rates²⁷.

Notes review. Patients will be asked to fill in a FREEPOST card to return documenting reconsultation (for worsening of symptoms, presentation with new symptoms and/or complications); this data will also be assessed by a review of the GP's notes. Although notes will be the main way of determining adverse outcomes these cards will provide additional information since sometimes patients get worse (after they have stopped filling in their diaries) and or adverse events do not get recorded in notes. We will relate whether adverse outcomes occur to the presence or absence of Streptococcus, clinical presentation and management

These clinical outcomes will provide information to confirm the sample size calculation for the phase 2 trial, and will allow exploration of the predictive value of throat swabs/rapid tests and clinical data for symptom resolution and reconsultation/complications.

3) In vitro study of RADTs.

The number of organisms harvested crucially determine the performance of the RADT¹², and two well taken samples from the same individual will predict the other results with a sensitivity of 83%-91%.¹⁴⁻¹⁶ Variation in RADT performance eliminating sampling bias will be assessed by in parallel in vitro studies (using different antigen loads comparable to the data coming from clinical studies, and also controls). The most recent and comprehensive of in vitro studies compared 16 tests but only included 4 of the 5 tests proposed¹⁷, and performed very few tests for each RADT. Thus more comprehensive comparative data is needed. As in the most recent in vitro study¹⁷we will compare the performance of RADTs using 4 strains of group A

As in the most recent in vitro study we will compare the performance of RADTs using 4 strains of group A beta haemolytic streptococci and a control strain (a group C streptococcus, or Moraxella), in three dilutions each $(10^5, 10^6, \text{ and } 10^7 \text{ Colony forming units per ml})$ corresponding to the range of growths normally seen from throat swabs in the community. We will perform 20 tests for each RADT at each dilution and for each strain (i.e. 200 tests for each RADT) which will provide similar power to the clinical study.

Assessing ease of use of RADTs by clinicians.

Most of the in vitro tests will be carried out by laboratory personnel who will rate ease of use, but we will also arrange a panel of 10 GPs and practice nurses - who will perform the tests in clinical practice – to perform four tests with each RADT, and the order of RADTs will be randomised. Several tests are required so that each clinician gets used to doing each test competently. For each test the clinician will document time to do the test, time to get the result (seconds), overall ease of use (on a five point Likert scale – very easy, easy, neither easy nor difficult, difficult, very difficult) and clarity of result (clear, unclear). After using all the RADTs each clinician will be asked to rank the RADTs in order of their overall preference.

4) Qualitative study.

The qualitative study will be based on grounded theory methodology ²⁸ to clarify patients' and primary care professionals' understanding and concerns about the use of RADTs in both phase 1 and 2. Grounded theory provides a framework for guiding decisions about sampling, data collection and analysis. It is furthermore a powerful method for discovering, understanding and developing explanatory concepts. A maximum variety sample of 15-20 patients and 15-20 GPs and nurses will be recruited. The purposive sample of patients will include both sexes, a range of ages, people from different socio-economic classes and minority ethnic groups. In keeping with grounded theory we will undertake further theoretical sampling to: a) extend information on the concepts identified, b) contrast/confirm/challenge the data already collected and c) to fill in any missing gaps in the data. An interview guide will be designed to reflect the study's objectives and existing literature in the area. The interview guide will be flexible and responsive to the respondent's narrative. This means that the results of earlier interviews will inform the kinds of questions asked at subsequent ones, in an iterative fashion. However,

we expect that the questions asked will explore the following general areas: the experience of sore throat or managing sore throat, decision-making or perceived decision making about consulting the general practitioner, perceived outcomes of consultations, decision-making about RADTs, and the consequences of treatment. In this way, the interview will follow the respondents agenda as far as possible, while remaining relevant to the issues of the use of RADTs. Open ended face-to-face, in-depth interviews will be carried out and audiotaped for transcription; field notes will be kept and memoranda written to aid with analysis. Transcripts will be analysed systematically through constant comparison analysis. Each interview will be analysed to identify primary issues and categories, a process known as open coding. These categories will then be compared with others within the transcript and across other transcripts, as well as to categories and concepts within the existing literature. The next stage, axial coding, will cross-link the concepts to generate new meanings and concepts. The final stage, selective coding, will cross-link the concepts to generate themes that will represent the most theoretically abstract unit of analysis from which theoretical explanations can be generated. The qualitative research will provide explanatory models clarifying understandings and concerns around the use of RADTs for both patients and doctors, sensitive to the context within which they experience and manage the illness. The model will inform the implementation of the randomised controlled trial – as well as the treatment and management of sore throat and the use of RADTs more generally. The qualitative work will start in phase 1 but continue in phase 2. The purpose of the qualitative work in the trial phase is twofold a) to help understand issues surrounding the process and experience of intervention early on in the trial to be able to modify trial procedures and trial documentation in the feasibility phase b) to understand attitudes and experiences of the health care professionals and patients involved in the trial that can help to explain the quantitative outcomes.

Outcomes from Phase I. These will be the estimates of sensitivity and specificity of RADTs and the Centor criteria (or modified criteria) compared to throat swab; ease of use of RADTs; a qualitative model to understand patients' and GPs perceptions and to inform strategies for phase 2; estimates and predictors of symptom resolution and adverse clinical outcomes.

Phase 2.

Planned interventions

Patients will be individually randomised using a web based randomisation service - with permuted block size of 3,6,9, and 12 being randomly chosen - to three groups:

- a) **RADT using the best RADT from phase 1.** Depending on phase I results, we provisionally assume the most efficient use of RADTs will be by targeting them to those with intermediate clinical scores. Thus those with low clinical scores (e.g. 0/1 Centor) will be unlikely to have bacterial infection; those with very high clinical scores (e.g. 4 Centor) much more likely to have bacterial infection. Only patients with a positive result from the RADT will be offered antibiotics. All patients as in the other groups will be advised to use analgesia (regular paracetamol and/or ibuprofen).
- b) A clinical scoring rule -either the Centor criteria, or the clinical rule developed from phase I (whichever performs best from phase I). The precise strategy to use the clinical score will be based on the results of phase I. However we anticipate that it is likely that antibiotics will not be offered at all to those with very low scores (e.g. Centor 1), for high scores (e.g. Centor 4) then immediate antibiotics will be advised unless symptoms settle rapidly within 48 hours, and for intermediate scores delayed antibiotics will be offered (see c). Such a modified use of the criteria is necessary since using a single cut-off leading to antibiotic use (e.g. 3+ Centor) from recent data nearly would mean 50% of patients are likely to need antibiotics.⁷

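### Phase I pairs each rapid test with culture of the same swab, so between-swab error largely drops out of the clinical study that is meant to include it, and the contrast with the in vitro study cannot estimate it

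*Protocol*

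**What the plan says.** Four parts of the protocol bear on this.

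- **Existing research, end of the sampling bias discussion.** An assessment of a rapid test "has to assess performance in clinical settings (which includes the performance of the test in the intended setting and sampling error"), and, as a separate element, "performance excluding sampling error (by assessing performance in standardised conditions"). The same discussion gives 83%-91% sensitivity for two well-taken swabs from one person compared with each other, and says that a test is unlikely to agree with the standard better than the standard agrees with itself.
- **Research Objectives, Objective 2, and Phase 1, In vitro study of RADTs.** The error from sampling bias is to be estimated through the in vitro work.
- **Phase 1, Clinical study of RADTs, Throat swabs and Analysis.** Each swab goes to both culture and one rapid test; piloting is said to show that "using the same swab for one RADT and the culture is both feasible, and minimises sampling variation". Adults give two double swabs (four tests), children one. The primary accuracy analysis "will be the analysis of 2x2 tables comparing RADTs with the results of the throat swab as the reference standard". Its rationale is that the rapid test replaces the throat swab.
- **Phase 1, Sample size.** The pairing is confirmed: "we will be comparing a rapid test versus the results from the same throat swab which should provide higher sensitivities". The planning range is 85%-95%, against 80%-90% in the better earlier studies. The +/-5% precision is chosen "to be confident that the sensitivity is not less than 80% which would be less useful clinically".

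**The concern.** The design logic needs a clinical arm that contains sampling error and an in vitro arm that does not; the difference between them would then speak to Objective 2. Same-swab pairing breaks this for one component. If the swab fails to pick up the organism from an infected throat, the rapid test and the culture are both negative and the patient is counted as a true negative. That failure never appears as a missed case.

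Two things are at stake. First, the between-swab part of Objective 2 is not estimated by the stated analysis, because it is largely absent from both arms. Second, the sensitivity reported as clinical performance will be higher than the one found against an independent swab. The protocol acknowledges the rise and moves its planning range up, but leaves the 80% usefulness level where it was without saying which kind of sensitivity is to be read against it.

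**Working it through.** **1. The protocol's own figures.** For a 95% interval of half-width 0.05, n = 1.96² × p(1 − p) / 0.05².

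- p = 0.85: 195.9, rounded up to 196. p = 0.90: 138.3, to 139. p = 0.95: 72.99, to 73.
- Divided by 0.25 prevalence: 784 / 556 / 292. Times five tests: 3920 / 2780 / 1460.
- Divided by 3.33 comparisons per patient: 1176 / 834 / 438.

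All stated figures reproduce, so there is no arithmetic error. With four comparisons per adult and two per child, 3.33 implies that two thirds of patients are adults.

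**2. The ceiling.** The Existing research section puts swab against swab at 83%-91% and treats the standard's agreement with itself as a limit on any test. The Sample size section plans for 85%-95%. The top of that range lies above the limit and is plausible only because between-swab disagreement has been taken out.

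**3. From same-swab to cross-swab sensitivity.** Let Se be the same-swab sensitivity and c the swab-to-swab sensitivity (83%-91%). Assume 100% specificity, which the protocol does not state. Two extremes bracket the answer.

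*Independent losses:* cross-swab sensitivity = c × Se.

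*Fully overlapping losses:* the rapid test's misses fall first on patients whose two swabs disagree, with the two swabs interchangeable. Cross-swab sensitivity is then the smaller of c and Se.

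| Same-swab Se | Independent, c = 0.83 to 0.91 | Fully overlapping | Whole range |
|---|---|---|---|
| 85% | 70.6% to 77.4% | 83% to 85% | about 71-85% |
| 90% | 74.7% to 81.9% | 83% to 90% | about 75-90% |
| 95% | 78.9% to 86.5% | 83% to 91% | about 79-91% |

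If specificity were 95%, a term (1 − c) × 0.05 is added to the independent case, which raises it by 0.4 to 0.9 percentage points.

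Under independence, a cross-swab estimate of 80% needs a same-swab value of 0.80 / 0.91 = 87.9% to 0.80 / 0.83 = 96.4%.

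**4. Precision of a cross-swab estimate.** At the planned numbers of positives, under independence, the half-widths are:

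- Se 85%, n = 196: 5.9 to 6.4 points.
- Se 90%, n = 139: 6.4 to 7.2 points.
- Se 95%, n = 73: 7.9 to 9.4 points.

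To hold +/-5% would take 270-320 / 228-291 / 180-257 positives per test. An adults-only comparison has fewer still: adults supply (2/3 × 4) / 3.33 = 80% of the tests, so, if prevalence is the same in adults and children, the half-widths grow by a further factor of 1/√0.8 = 1.12. Even at the fully overlapping extreme, where the smallest full-sample half-width is 5.0 points, the adults-only figure is about 5.6.

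**The case against.** The strongest reply is that same-swab pairing is deliberate, piloted and disclosed. The Analysis section defines the question as whether the rapid test can stand in for the throat swab, and for agreement with culture of that specimen the estimate is not biased. That stands, and is why the same-swab tables should remain primary.

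Nor does pairing remove all sampling error. The number of organisms harvested still varies from swab to swab and still produces results that are negative on the rapid test and positive in broth culture. The in vitro study fixes the load, so the contrast remains informative about load-related performance. Only between-swab discordance is lost. That also stands.

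Three stronger readings are tempting, and the documents do not support them.

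- *That Phase I has an 80% pass mark which a biased figure would clear.* The >80% criterion in the Analysis section selects candidate tests from earlier studies. In the Sample size section, 80% explains the chosen precision. No rule makes entry to Phase II depend on it.
- *That the wrong test may go into Phase II.* That choice is of the best test, a comparison among tests, and pairing applies to all five alike. Under independence every test is multiplied by the same factor and the order is unchanged.
- *That a same-swab 85% must fall below 80%.* This needs independent losses. The protocol itself ties rapid-test performance to colony count, so low-load patients may account for both kinds of loss. With full overlap, the cross-swab value is 83-85%.

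Finally, secondary tables are often left to a statistical analysis plan. The absence of such a table is not the finding here. The protocol states a requirement and an objective that its own described design does not meet for between-swab error, and adds no text to reconcile them.

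**Conclusion.** The point holds as an unreconciled contradiction with a practical consequence. The clinical arm is said to include sampling error, but same-swab pairing largely takes the between-swab part out, so that part of Objective 2 goes unestimated. The reported sensitivity will be sound for agreement with the same specimen and optimistic against an independent swab. The direction is conceded in the Sample size section.

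The size is uncertain. The ranges in the table rest on the protocol's 83%-91%, on assumed perfect specificity, and on an unknown degree of overlap between the two losses. At every planning value the range spans 80%, so the same-swab result alone cannot show whether a test stays above that level against an independent swab. The change should be made, but it does not call the selection of the Phase II test into question.

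**What to change.** Keep the same-swab 2x2 tables as the primary analysis for the replacement question. Add a prespecified secondary analysis with two parts:

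1. In adults, the rapid test on a swab from one double swab against culture from the other double swab. Report culture against culture as the ceiling, and use patient-clustered standard errors.
2. Sensitivity and specificity against a patient-level reference of culture positive on any swab, reported separately for adults (four swabs) and children (two swabs), since the definition depends on the number of swabs.

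State that the between-swab part of Objective 2 is estimated from these analyses and that the in vitro study covers load-related performance. Say that the 80% usefulness level is read against the cross-swab estimate as well as the same-swab one, and align the wording in the Existing research section with this.

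The cost is some analysis text; every swab is already to be cultured, so no new samples are needed. The added sensitivities will look less favourable, and their intervals will be wider than +/-5% at the planned numbers. That should be stated openly rather than met by enrolling more patients.
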